The purpose of this study is to prospectively compare preoperative (neoadjuvant) SRS/SRT to postoperative (adjuvant) SRS/SRT in patients undergoing surgical resection for brain metastases.

Hypothesis, Objectives, and Outcomes

We hypothesize that neoadjuvant SRS/SRT prior to surgical resection of brain metastases will result in improved freedom from Central Nervous System (CNS) events when compared to adjuvant SRS/SRT after surgical resection.

Primary Objectives

- Our primary objectives are: (1) to determine the *Time to a Central Nervous System* (*CNS*) *Composite Event* (*CE*) in subjects who receive either neoadjuvant (preoperative) SRS/SRT or adjuvant (post-operative) SRS/SRT for their brain metastases, and (2) to compare the two treatment arms for evidence of improved Time to a CNS CE among subjects who received neoadjuvant SRS/SRT.
 - A CNS CE will consist of one of the following three events: Local Recurrence (LR) of the treated lesions, symptomatic radiation necrosis (SRN) to the treated lesions, or development of leptomeningeal disease (LMD). See below for detailed definitions of LR, SRN, and LMD.
 - Time to a CNS CE, the primary outcome, will be measured as the time from the date of randomization to the date of a documented LR, SRN, or LMD, whichever occurs first.
 - Death before occurrence of a CNS CE will be treated as a competing risk. Study participants who are alive and have yet to experience a CNS CE at their last evaluation will be right-censored for Time to CNS CE on the date of their last evaluation.

Secondary Objectives related to the Primary Objective. Some of our secondary objectives include (a) determining in each study subject the *secondary outcomes* listed below, and (b) comparing the treatment arms for evidence of improvements in these secondary outcomes.

- Index lesion local recurrence (ILLR), a component of CNS CE, will be defined as the development of new nodular contrast enhancement in the surgical bed compared with the immediate postoperative MRI.
- Non-index lesion LR, also a component of CNS CE, will be defined as an increase of more than 25% in the size of any treated non-resected brain lesion.

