Other Secondary Objectives include determining the other secondary outcomes described below, and comparing treatment arms for improvements with neoadjuvant SRS/SRT in (a) the rates of secondary yes/no outcomes such as Local Control, or (b) the 6-month, 12-month, 18-month, month rates of secondary time-to-event outcomes such as Duration of Local Control:

- Local Control.
 - Local Control will be defined as Complete Response [CR], Partial Response [PR], or Stable Disease [SD] of the index lesion resulting from the assigned treatment. It will be determined at the first evaluation following successful completion of either neoadjuvant or adjuvant SRS/SRT of all metastatic lesions and surgical resection of the index lesion.
 - Stratified by GTR or STR, piecemeal vs en bloc resection

- Treatment Failure will be defined either as Progressive Disease [PD] during the assigned treatment, or as the absence of Local Control at the first evaluation following successful completion of the assigned treatment.
- Duration of Local Control (DLC) will be measured as the time from the date when Local Control is first documented to the date when:
 - the treated lesions show documented evidence of LR or PD, or
 - the patient undergoes whole-brain radiotherapy, repeat SRS, repeat surgical intervention
- Time to distant in-brain failure.
 - Distant in-brain failure (DiBF) will be defined as the occurrence of any new parenchymal lesion outside of the planning target volume.
 - Time to DiBF will be measured as the time from the date of randomization to the date of occurrence of the DiBF. Death before occurrence of DiBF will be treated as a competing risk. Study subjects who are alive and free of DiBF at their last evaluation will be right-censored for Time to DiBF on the date of their last evaluation.
- Overall survival.
 - Overall survival (OS) will be measured as the time from the randomization date to the date of death for any reason. Study participants who are still alive at last follow-up will be right-censored for OS on the date of their last follow-up.
- Time to systemic therapy.
 - Time to initiation or re-initiation of systemic therapy will be measured as the time from the date when the assigned treatment (neoadjuvant versus adjuvant SRS/SRT) is successfully completed to the date when the systemic therapy is initiated or re-initiated.

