Data Safety Monitoring Plan: The study will be monitored by the investigators to ensure that the rights and well-being of human subjects are protected, that the data are accurate, complete and verifiable from source documents and that the trial is conducted in compliance with currently approved protocol/amendments. The PI and sub-Investigators will review study conduct on an ongoing basis. The PI will assure that all protocol deviations, AEs, and SAEs are reported to the IRB according to the applicable regulatory requirements.

Specimen Handling and Storage

Tumor specimens will be collected from surgical resection and stored by the Department of Pathology and kept as part of standard of care. No samples will be collected specifically for use in this study at this time.

Data Analysis

Statistical analysis plan

Patient characteristics will include patient demographics, disease characteristics of the primary tumor, and relevant characteristics (number, location, size, etc.) of the brain metastases being treated. Patient characteristics will be summarized by treatment arm with medians, quartiles, and ranges for numeric characteristics, or with numbers and percentages for category characteristics. Each characteristic then will be assessed for imbalance between treatment arms with Wilcoxon's rank-sum test for numeric characteristics. The imbalance assessments will consist of 2-sided tests that employ the standard α =0.05 significance level.

Time to a CNS CE, the primary outcome, will be visualized with Cumulative Incidence (CI) curves computed using Kaplan-Meier methodology, summarized by treatment group as CI proportions at 6, 12, and 18 months, and compared for difference using the Fine and Gray model for equality of CI functions when death before a CNS CE is treated as a competing risk. Times to each of the individual CNS events (LR, SRN, LMD, DiBF, and WBRT) will be analyzed the same way, except that each Fine and Gray model will have the competing risk be death before the individual event being analyzed. Overall survival will be visualized using standard Kaplan-Meier curves and compared for differences via the log-rank test. Because this is a pilot study, all time-to-event outcomes will be compared for evidence of improvement on the pre-operative SRS/SRT arm using 1-sided tests that employ an α =0.10 significance level.

Sample size, power, and study duration

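### The blanket 1-sided rule gives the overall survival test no way to declare harm, and no survival hazard ratio or interval is planned

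*Combined protocol and SAP*

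**What the plan says.** Under Data Analysis, Statistical analysis plan, OS has its own sentence: "Overall survival will be visualized using standard Kaplan-Meier curves and compared for differences via the log-rank test". The next sentence, which gives the study's pilot status as the reason, sets the sidedness for everything: "all time-to-event outcomes will be compared for evidence of improvement on the pre-operative SRS/SRT arm using 1-sided tests", with alpha at 0.10. The Other Secondary Objectives point the same way, "comparing treatment arms for improvements with neoadjuvant SRS/SRT". The definition of OS is conventional: "Overall survival (OS) will be measured as the time from the randomization date to the date of death for any reason".

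The study hypothesis concerns CNS events only, namely that neoadjuvant treatment "will result in improved freedom from Central Nervous System (CNS) events when compared to adjuvant SRS/SRT after surgical resection". The Primary Objectives treat death before a CNS composite event as a competing risk. No OS hazard ratio, confidence interval, non-inferiority margin or harm boundary is given. The Data Safety Monitoring Plan relies on ongoing review by the investigators and describes no survival comparison.

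Time to systemic therapy is defined under Other Secondary Objectives: "Time to initiation or re-initiation of systemic therapy will be measured as the time from the date when the assigned treatment" is completed to the start or restart of that therapy. No favourable direction is stated. It is also absent from the list of individual outcomes given a model ("Times to each of the individual CNS events (LR, SRN, LMD, DiBF, and WBRT) will be analyzed the same way"), so only the general 1-sided sentence governs its test.

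**The concern.** A 1-sided 10% test is a defensible choice for the primary outcome of a phase II pilot with a directional hypothesis. The same rule is then carried over to OS, for which the documents state no directional hypothesis and where a detriment would matter at least as much as a gain. With rejection possible only for benefit, a non-significant OS result cannot distinguish no difference from harm, and no interval is planned that would do so.

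OS is also needed to read the primary result. A Fine and Gray comparison works on cumulative incidence, and a patient who dies can no longer have a CNS event. Higher mortality on one arm therefore lowers that arm's CNS event incidence even when its CNS event hazard is unchanged. An apparent CNS gain has to be read beside a survival comparison that is able to show harm.

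For time to systemic therapy the difficulty is different. A shorter time could mean that planned treatment resumed sooner, or that progression forced an earlier start. A 1-sided test for improvement is undefined until the plan says which direction counts as improvement.

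**Working it through.** The plan gives no power or event count for OS. Its only such figures (80.7% power, 26.0 events) belong to the primary outcome and do not bear on this point.

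**Inputs from Sample size, power, and study duration.** 52 patients per arm; 3 years of accrual and 1.5 years of minimum follow-up, so follow-up is taken as uniform on 1.5 to 4.5 years; competing death rate 32% per year; control CNS event rate 25% per year, pre-operative rate 12.5%.

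**Assumptions.** The 32% is stated for death before a CNS event. The documents give no all-cause death rate, so 32% is used as a stand-in for the control arm. It is read either as a hazard (0.32) or as an annual probability (hazard −ln 0.68 = 0.386). Follow-up is either full or cut at 18 months, the limit the Follow-up section sets for including MRIs. Survival is exponential.

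**Formulas.** Probability of death with full follow-up: P(λ) = 1 − [exp(−1.5λ) − exp(−4.5λ)]/(3λ). By 18 months: P(λ) = 1 − exp(−1.5λ). Expected deaths D = 52[P(λ) + P(λ·HR)]. Log-rank shift θ = ½√D·ln(HR). Planned test significant for benefit: Φ(−θ − 1.2816). A 2-sided 5% test detecting the harm: Φ(θ − 1.96).

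**Worked case, HR 1.5 against the pre-operative arm, hazard 0.32, full follow-up.** P(0.32) = 1 − (0.6188 − 0.2369)/0.96 = 0.602, or 31.3 deaths. P(0.48) = 1 − (0.4868 − 0.1153)/1.44 = 0.742, or 38.6 deaths. D = 69.9 and θ = ½ × √69.9 × 0.4055 = 1.695. Planned test: Φ(−2.977) = 0.15%. 2-sided 5% test: Φ(−0.265) = 39.6%.

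| Reading of 32% | Follow-up | Deaths, HR 1.5 | Planned test significant | 2-sided 5% power, HR 1.5 | Deaths, HR 1.75 | 2-sided 5% power, HR 1.75 |
|---|---|---|---|---|---|---|
| hazard | full | 69.9 | 0.15% | 39.6% | 72.4 | 66.3% |
| hazard | 18 months | 46.5 | 0.39% | 28.2% | 49.4 | 50.2% |
| probability | full | 76.4 | 0.11% | 42.5% | 78.6 | 69.9% |
| probability | 18 months | 53.0 | 0.29% | 31.4% | 55.9 | 55.3% |

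**Effect of excess deaths on the primary outcome.** With CNS event hazard c and death hazard d, the 18-month cumulative incidence is c/(c+d) × [1 − exp(−1.5(c+d))]. Hold c at 0.25:

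- d = 0.32: 0.4386 × (1 − 0.4253) = 25.2%
- d = 0.48: 0.3425 × (1 − 0.3345) = 22.8%
- d = 0.64: 0.2809 × (1 − 0.2632) = 20.7%

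For scale, the design effect itself (c = 0.125, d = 0.32) gives 0.2809 × (1 − 0.5130) = 13.7%. A death hazard ratio of 1.5 thus produces 2.4 points of spurious reduction, against the 11.5 points that the design targets.

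**Price of the change if survival is truly better.** At a hazard ratio of 1/1.5 (hazard 0.32, full follow-up), D = 55.4 and θ = 1.509. Power for benefit is Φ(1.509 − 1.2816) = 59% with the 1-sided 10% test and Φ(1.509 − 1.96) = 33% with a 2-sided 5% test.

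**The case against.** The best defence is that the study is a pilot, says so when it sets the rule, and keeps OS secondary. A detriment would not be invisible either: Kaplan-Meier curves are planned, rates at 6, 12 and 18 months are compared, adverse events are an outcome, and serious events go to the IRB. A 1-sided p-value near 1 also carries the information. This stands in part. It defeats the inference that harm could not show at all. What is missing is a formal comparison in that direction and an interval. The landmark comparisons do not supply them, because they too are framed as improvements.

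Three further readings are tempting and unsupported.

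- A reader might see a contradiction between the OS sentence, which speaks of differences, and the 1-sided rule. The same paragraph uses nearly the same phrase for the primary outcome, which is plainly 1-sided, so the phrase is generic.
- A reader might infer from the schedule that pre-operative treatment is expected to worsen survival because surgery can fall later on that arm. The treatment-arm table gives maximum windows, not expected delays. Radiation on the post-operative arm can fall as late as about day 45 (15 + 30), and the Potential risks section names no survival detriment.
- A reader might infer that the sign chosen for systemic therapy could produce opposite significant findings. Reversing it turns p into 1 − p, so both directions cannot be significant.

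It is also fair that a 2-sided 5% test would still miss a hazard ratio of 1.5 more often than not. The larger gain is the reported interval.

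**Conclusion.** The point holds. As written, the OS test cannot reject for harm, and nothing planned quantifies a survival difference with its uncertainty. At a death hazard ratio of 1.5 against the pre-operative arm, the planned test is significant with probability 0.1% to 0.4%, and only in the wrong direction. A 2-sided 5% test has 28% to 43% power, or 50% to 70% at a hazard ratio of 1.75. Without it, a detriment of that size would be seen only descriptively.

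These figures rest on taking 32% per year as all-cause mortality, which the documents do not state, and on exponential survival. The absence of a rejection region for harm rests on neither. The distortion of the primary outcome through competing deaths is real but moderate: about a fifth of the design effect at a hazard ratio of 1.5 (2.4/11.5). The systemic-therapy gap is genuine and smaller: the direction of improvement is simply undeclared.

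**What to change.** In the Statistical analysis plan, limit the sentence that sets 1-sided testing so that OS is exempt. Compare OS with a 2-sided log-rank test and report the hazard ratio with a 2-sided 95% confidence interval. Keep the 1-sided 10% test for time to CNS composite event, and present the OS result beside it.

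Compare time to systemic therapy 2-sided as well, with an interval. Splitting it by reason for starting is not needed: that would require collecting the reason and handling each type of start as a competing event for the other.

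The cost is a small text change to the plan, with no effect on the primary test, its power or the 104 patients. The drawback is that a genuine OS benefit becomes harder to call significant (59% falling to 33% in the example worked above), on a secondary outcome that does not drive the sample size. The hazard ratio and interval are informative in either direction.

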Sample-size calculations are informed by results from Patel et al.'s retrospective study.⁶ Based on their results, we expect that the post-operative SRS/SRT arm will have an average CNS CE rate of approximately 25% per year, accompanied by an average competing-risks rate of approximately 32% per year (where the competing risk is death before the CNS CE). Sample-size calculations are also informed by the fact that UAMS typically sees approximately 50 patients per year who should meet this study's eligibility requirements.

To meet its objectives, our randomized Phase II pilot study of pre-operative SRS/SRT versus post-operative SRS/SRT needs to have >80% power to detect a 50% decrease in the rate of CNS CE on the pre-operative SRS/SRT arm using a 1-sided test at 10% alpha. The power of tests under the Fine and Gray competing-risks model is well-approximated by the power of log-rank tests calculated with the competing-risk rate represented as non-zero dropout rates on each study arm. To calculate power of 1-sided log-rank tests at 10% alpha, we implement the following assumptions in PASS 16 software⁹:

- Accrual duration will be three years while minimum follow-up will be 1.5 years, leading to a total study duration of 4.5 years.
- The post-operative SRS/SRT arm will have a CNS CE rate that averages 25.0% per year.
- The pre-operative SRS/SRT arm will have a CNS CE rate that averages 12.5% per year, or half the rate on the post-operative SRS/SRT arm.
- Both arms will have a dropout rate of 32% per year due to the competing risk.
- The crossover rate from one arm to the other will be zero on both arms.
- Sample sizes will be equal on both arms.

Under these assumptions, a sample size of 52 subjects per treatment arm (a total of 104 subjects) is calculated to provide the 1-sided log-rank test (and thus the equivalent Fine and Gray test) with 80.7% power at 10% alpha to detect a 50% reduction in the CNS CE rate with pre-operative SRS/SRT relative to the CNS CE rate with post-operative SRS/SRT. Under the same assumptions, the number of CNS CE's is projected to reach expected values of 8.6 with pre-operative SRS/SRT and 17.4 with post-operative SRS/SRT for a total expected value of 26.0 by the end of the study.

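### The 80.7% power belongs to a log-rank test; the planned Fine and Gray test has about 3 to 4 points less under the plan's own assumptions and misses the >80% requirement

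*Combined protocol and SAP*

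**What the plan says.** Under *Data Analysis, Statistical analysis plan*, time to a CNS composite event is to be "compared for difference using the Fine and Gray model for equality of CI functions". Deaths that precede the event count as the competing risk.

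Under *Sample size, power, and study duration*, the trial "needs to have >80% power to detect a 50% decrease in the rate of CNS CE" with the experimental treatment; the test is one-sided with alpha 0.10. The link between the planned test and the calculation is one sentence: "The power of tests under the Fine and Gray competing-risks model is well-approximated by the power of log-rank tests calculated with the competing-risk rate" entered as dropout. The yearly CNS event rates are set at 25% for the comparator and 12.5% for the experimental treatment. Mortality is handled as loss to follow-up: "Both arms will have a dropout rate of 32% per year due to the competing risk".

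For 52 patients in each group, the section credits "the 1-sided log-rank test (and thus the equivalent Fine and Gray test) with 80.7% power at 10% alpha". It shows no power calculation for Fine and Gray itself.

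**The concern.** Entering deaths as dropout removes patients from the risk set when they die. The resulting log-rank test compares cause-specific hazards. Fine and Gray keeps patients who died without a CNS event in the risk set and compares subdistribution hazards. The two hazard ratios coincide only in special cases, and a treatment that halves the CNS event rate without changing mortality is not one of them.

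The stated power exceeds the plan's threshold by 0.7 points. A loss of a few points in passing from one test to the other therefore decides whether the design meets its own requirement. The only power figure offered for the primary analysis belongs to a test that will not be its primary analysis.

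**Working it through.** **Inputs (all from the sample-size section).** 52 per arm, 1:1; accrual over 3 years (taken as uniform), minimum follow-up 1.5 years, so follow-up of 1.5 to 4.5 years; yearly CNS event rates of 25% and 12.5%; yearly death rate of 32% in both arms; no crossover; one-sided alpha 0.10. The plan does not say whether a yearly percentage is a hazard or a one-year proportion p, for which the hazard is −ln(1−p). Three readings were run, with constant hazards.

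**Step 1: the plan's log-rank figure.** With event hazard λ, death hazard μ and h = λ + μ, expected events per arm are

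52 × (λ/h) × [1 − (e^(−1.5h) − e^(−4.5h))/(3h)].

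Schoenfeld power is Φ(|ln HR| × √d / 2 − 1.2816), where d is total events.

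| Reading | λ post / λ pre / μ | HR | Events post + pre | Schoenfeld power |
|---|---|---|---|---|
| All hazards | 0.250 / 0.125 / 0.320 | 0.500 | 18.2 + 10.5 = 28.6 | 71.7% |
| All one-year proportions | 0.288 / 0.134 / 0.386 | 0.464 | 18.7 + 10.3 = 29.0 | 78.4% |
| Mixed: events as proportions, death as hazard | 0.288 / 0.134 / 0.320 | 0.464 | 20.1 + 11.1 = 31.1 | 80.5% |

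(Totals are summed before rounding.) The mixed reading comes within 0.2 points of 80.7%. The stated 26.0 events are not reproduced by any of the three.

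**Step 2: why the two tests differ.** The subdistribution hazard in an arm is λ × w(t). Here w(t) is the share of the Fine and Gray risk set still alive:

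w(t) = e^(−ht) / [1 − (λ/h)(1 − e^(−ht))].

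The arm with fewer CNS events keeps a larger living share, so its subdistribution hazard falls less. All-hazards reading at 3 years: w = 0.332 pre-operative and 0.282 post-operative, so the ratio is 0.5 × 0.332/0.282 = 0.59. The same formula gives 0.50 at time zero, 0.51 at 1 year and 0.52 at 1.5 years. Averaged over the trial in large samples, the hazard ratio moves from 0.50 to 0.52 (all hazards) or from 0.46 to 0.49 (all proportions).

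**Step 3: power of both tests on the same simulated trials.** The log-rank test censors deaths. The Fine and Gray score test keeps deaths at risk until their administrative censoring time; a version with inverse-probability-of-censoring weights gave nearly the same power. Ranges are over repeat simulations of 12,000 to 40,000 trials.

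| Reading, 52 per arm | Log-rank | Fine and Gray | Gap (points) |
|---|---|---|---|
| All hazards | 70.0–70.7% | 67.3–67.5% | 2.7–3.5 |
| All one-year proportions | 76.7–77.8% | 72.9–73.8% | 3.7–4.0 |
| Mixed | 78.8–79.4% | 75.6–76.0% | 3.0–3.8 |

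Under the null both tests reject in about 10% of trials, so the gap is not a difference in size.

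**Step 4: other readings.**

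- Rates as 18-month proportions: 80.7% v 76.6%.
- Hazards tuned to give the stated 17.4 and 8.6 events: 80.3% v 77.5%.
- 25% and 12.5% as one-year cumulative incidence: 82.3–83.4% v 77.9–79.6%.

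Over all readings tried, the gap is 2.7 to 4.4 points and Fine and Gray power runs from 67.3% to 79.6%.

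**Step 5: granting the 80.7%.** The number per arm was raised until log-rank reached about that figure. With proportions (58–59 per arm), log-rank 80.4–81.2% goes with Fine and Gray 76.9–77.3%. With hazards (72 per arm), 80.8% goes with 77.5%.

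**The case against.** **The gap depends on long follow-up.** It builds up late, and the Follow-up paragraph of *Study Design and Procedures* limits the MRIs counted in the results to 18 months. With follow-up capped there, simulation gives log-rank v Fine and Gray of 59.0% v 58.1% (hazards), 68.1% v 67.0% (proportions) and 68.7% v 67.2% (mixed). The gap shrinks to about 1 to 1.5 points. This is correct, but it does not rescue the claim. The power section assumes follow-up to 4.5 years, and under the cap Fine and Gray power is 58% to 67%, further below the requirement.

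**Fine and Gray is not the only cause of the shortfall.** In all three main readings the simulated log-rank test is itself below 80% at 52 per arm, and the choice of reading moves power by about 9 points, more than the gap between tests. The stated events and power also do not fit together: 26 events with a hazard ratio of 0.5 give Schoenfeld power of 68.6%. This stands as a separate and possibly larger problem. The present point survives it, because Fine and Gray still falls to about 77% when 80.7% is granted.

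**This is a pilot, and the plan calls the match an approximation.** A pilot can accept 77%. But this plan sets its own >80% requirement, reports power to one decimal place and goes on to call the tests equivalent. An approximation that is off by several times the claimed margin cannot support that claim.

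**Conclusion.** The concern holds. Under the plan's own power assumptions, Fine and Gray has about 3 to 4 points less power than the log-rank test used to size the trial (2.7 to 4.4 over all readings). The primary test is below 80% in every reading: about 77% if 80.7% is right for log-rank, and 67% to 76% under the three main readings at 52 per arm. The result assumes constant hazards, uniform accrual and no treatment effect on death; the last is how the plan set up its calculation. The loss is modest and does not invalidate the design, but the stated power of the primary analysis is wrong as written.

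**What to change.** 1. Remove the parenthetical claim that the Fine and Gray test is equivalent, and the sentence saying log-rank power approximates it well.
2. State whether each yearly rate is a hazard or a one-year proportion, and use the follow-up that the primary analysis will actually include.
3. Simulate both competing hazards, apply the planned one-sided Fine and Gray test, and report that power. Expect about 77% if the log-rank figure really is 80.7%, and less otherwise.
4. Bring the >80% requirement into line: either keep 104 patients and say that the pilot accepts the lower power, or enlarge the trial.

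Keeping 104 costs one simulation and a few reworded sentences, with no extra patients; the stated power becomes 3 to 4 points or more less favourable. For comparison, scaling 52 by the squared ratio of (0.8416 + 1.2816) to (z of the simulated power + 1.2816) puts 80% Fine and Gray power at roughly 61 per arm (mixed), 66 (proportions) or 79 (hazards), with follow-up of 1.5 to 4.5 years. These are approximations.

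### The stated 80.7% power and the 17.4 and 8.6 expected events do not follow together from the stated 25% versus 12.5% per year on any natural reading of those rates

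*Combined protocol and SAP*

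**What the plan says.** All of this is in the combined protocol and SAP, Data Analysis, under Sample size, power, and study duration.

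- **Requirement.** To meet its objectives the trial "needs to have >80% power to detect a 50% decrease in the rate of CNS CE" with a 1-sided test at 10% alpha.
- **Control event rate.** The assumption for the comparator is: "The post-operative SRS/SRT arm will have a CNS CE rate that averages 25.0% per year".
- **Experimental event rate.** The next assumption halves that figure: "The pre-operative SRS/SRT arm will have a CNS CE rate that averages 12.5% per year, or half the rate" of the other arm.
- **Competing death.** This enters the calculation as loss: "Both arms will have a dropout rate of 32% per year due to the competing risk".
- **Design.** Three years of accrual, 1.5 years of minimum follow-up, no crossover, equal arms, 52 per arm.
- **Claimed results.** A 1-sided log-rank test "with 80.7% power at 10% alpha to detect a 50% reduction in the CNS CE rate", and, on the same assumptions, "expected values of 8.6 with pre-operative SRS/SRT and 17.4 with post-operative SRS/SRT for a total expected value of 26.0".
- **Link to the planned test.** Fine and Gray power is first described as "well-approximated by the power of log-rank tests calculated with the competing-risk rate represented as non-zero dropout rates on each study arm". The result is then given for "the 1-sided log-rank test (and thus the equivalent Fine and Gray test".

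The section does not say whether the three rates are hazards or proportions, or over what period the event rates are averaged.

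**The concern.** The section gives enough inputs to recompute both outputs, and two quick checks fail.

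First, the event split. If the hazard is halved and dropout is equal, pre-operative patients stay at risk longer, so that arm must have more than half of the control events. This holds for any accrual pattern and any shape of the control hazard. The plan's ratio is 8.6/17.4 = 0.494 (0.490 to 0.499 allowing for rounding).

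Second, 26.0 events are too few for 80.7% power at a halved hazard.

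This calculation is the only power justification for 104 subjects, and the recruitment target rests on it. If the inputs and outputs disagree, a reader cannot tell which effect the trial was sized for or whether the plan's own power requirement is met. A null result could not then be set against a known detectable effect.

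**Working it through.** **Inputs (from the sample-size section).** n = 52 per arm; event rates 25.0% and 12.5% per year; dropout 32% per year in both arms; accrual 3 years; follow-up 1.5 to 4.5 years; 1-sided alpha 0.10 (z = 1.2816).

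**Assumptions added here.** Uniform accrual and constant hazards. A proportion p averaged per year over T years becomes the hazard -ln(1 - pT)/T.

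**Formulas.** With event hazard h and dropout hazard d, expected events per arm are

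E = n × h/(h+d) × [1 - (exp(-1.5(h+d)) - exp(-4.5(h+d))) / (3(h+d))].

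Schoenfeld power with D total events is Φ(½√D × |ln HR| - 1.2816). The Lakatos calculation sums over small time intervals. With D_i the events in an interval and φ_i the ratio of numbers at risk, its mean statistic is Σ D_i[φ_i/(1+φ_i) - φ_i·HR/(1+φ_i·HR)] / √(Σ D_i φ_i/(1+φ_i)²).

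**Attempt to reproduce the plan, rates as hazards (HR 0.50).**
- Post-operative: h+d = 0.57; 52 × 0.4386 × [1 - (0.4253 - 0.0769)/1.71] = 18.2.
- Pre-operative: h+d = 0.445; 52 × 0.2809 × [1 - (0.5130 - 0.1350)/1.335] = 10.5.
- Total 28.6. Schoenfeld: ½√28.63 × 0.6931 - 1.2816 = 0.573, power 71.7%. Lakatos: 70.5%.

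**All readings.**

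| Reading | HR | Events post / pre | Ratio pre/post | Log-rank power, Lakatos to Schoenfeld |
|---|---|---|---|---|
| Plan as stated | – | 17.4 / 8.6 | 0.494 | 80.7% |
| All hazards | 0.500 | 18.2 / 10.5 | 0.577 | 70.5-71.7% |
| Events hazards, dropout annual proportion | 0.500 | 16.9 / 9.7 | 0.573 | 68.1-69.4% |
| All annual proportions | 0.464 | 18.7 / 10.3 | 0.548 | 77.0-78.4% |
| Events annual proportions, dropout hazard | 0.464 | 20.1 / 11.1 | 0.552 | 79.2-80.5% |
| All averaged over 1.5 years (an assumed period) | 0.442 | 18.9 / 10.0 | 0.529 | 80.5-82.0% |

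The readings that come close on power have about 3 to 5 events too many. The one that comes close on the total (26.6) has power 11 to 13 points too low.

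**From the event total alone.** At HR 0.50, 26.0 events give ½√26 × 0.6931 - 1.2816 = 0.486, power 68.6%. Reaching 80.7% needs 4 × (1.2816 + 0.8669)² / 0.6931² = 38.4 events. At HR 0.464 the figures are 75.0% and 31.3 events.

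**Working back from 17.4 and 8.6.**

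| Dropout hazard | Post hazard | Pre hazard | HR | Lakatos power |
|---|---|---|---|---|
| 0.32 | 0.236 | 0.100 | 0.422 | 80.2% |
| 0.36 | 0.250 | 0.105 | 0.420 | 80.5% |
| 0.386 | 0.259 | 0.109 | 0.419 | 80.7% |

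The stated events and power therefore agree with each other at a hazard ratio of about 0.42, a hazard reduction of about 58%.

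**Fine and Gray.** Simulated power (60,000 trials per scenario), log-rank then Fine and Gray, in the order of the first four readings: 70.5/67.2, 68.4/65.1, 76.7/73.1 and 79.3/75.7. The gap is 3.3 to 3.6 points. If the three rates are instead one-year cumulative incidences, Lakatos power is 81.0% or 83.3% against Fine and Gray power of 76.0% or 73.5%, a gap of 5 to 10 points.

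**The case against.** The plan never states a hazard ratio of 0.50. It speaks of rates that average a given value per year and of a 50% reduction in the rate. Halving a proportion reduces the hazard by more than half, and the more so the longer the averaging period. With 1.5-year averages, log-rank power is 80.5-82.0%; with dropout left as an annual proportion or a hazard it is 82.1-83.5% or 84.1-85.4%. Separate averaging periods come close to all three outputs: 1.90 years for events and 2.34 years for dropout give 17.4 and 8.8 events with 80.7% power. The software run has not been seen, so an undocumented input may explain the figures.

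Much of this stands, and it rules out three stronger conclusions that a reader might draw.

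- **That the trial is underpowered.** Power is below 80% on most direct readings but above it on some longer averages, and the documents do not say which applies.
- **That the 25% control rate must be wrong.** A control hazard of 0.25 with a dropout hazard of 0.36 gives 17.4 and 8.6 events. A dropout hazard of 0.36 is not a natural reading of 32% per year, but the control rate cannot be singled out as the faulty input.
- **That no averaging scheme could produce the figures.** Contrived ones come close, and a search over invented schemes cannot exclude every one.

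What the objection does not rescue is the text. The separate periods are stated nowhere, the example above still misses 8.6, and at a hazard ratio of about 0.42 it does not halve the hazard.

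**Conclusion.** Wrong as written. The plan presents 80.7% power and 17.4 plus 8.6 events as consequences of its listed assumptions, and no natural reading of those assumptions gives them together. On the four hazard and annual-proportion readings, expected events are 16.9-20.1 and 9.7-11.1 and log-rank power is 68% to 80.5%. At a halved hazard, 26.0 events support about 69%.

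The figures rest on uniform accrual and constant hazards. The event-split argument needs neither, only a halved hazard and equal dropout. The cause of the mismatch, and whether the requirement of more than 80% is met, cannot be settled without the software run.

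A lesser point stands too. Log-rank power is an approximation to Fine and Gray power, not its equivalent. In the simulations the Fine and Gray power is lower, by an amount that depends on the scale of the rates.

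**What to change.** 1. Recover the software run. State the scale (hazard or proportion) and averaging period of the event and dropout rates, and the hazard ratio entered.
2. On that scale, restate expected events per arm and log-rank power for 25% versus 12.5%; the table of readings gives the values to expect. Alternatively, state the hazard ratio that 104 subjects detect with 80% log-rank power: by Lakatos 0.434 for hazards, 0.443 for annual proportions and 0.446 for 1.5-year averages.
3. Correct any input bullet that differs from the run.
4. Only if power on that scale is below 80%, withdraw the claim that 104 subjects give more than 80% power for a 50% reduction.
5. Replace the description of the Fine and Gray test as equivalent with a separately computed Fine and Gray power. Do not substitute a fixed deduction from the log-rank figure.

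The cost is retrieving one run and rewording one section. The downside is that the stated power may become less favourable, or the stated target effect larger. The sample size and the test do not change. If the sponsor would rather keep the requirement than withdraw the claim, that is a separate design decision: by Schoenfeld, at least 80% power needs about 69 per arm (138) if the rates are hazards, or 55 per arm (110) if they are annual proportions.
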